### 11.7 REPORTING AND FOLLOW-UP OF PREGNANCIES

All participants who are determined to be pregnant after enrollment will be discontinued from the study. Advice on the risk of smoking and smoking cessation will be provided by the study doctor (or qualified staff) and participants will be referred to the respective health care facility/health care provider for further support.

The Investigator is responsible for informing the IRB of any pregnancy that occurs during the study according to local regulations.

### 11.8 ADVERSE EVENT LEADING TO DISCONTINUATION

If a participant is discontinued from the study because of an AE, the Investigator or designee will follow up until the AE(s) has/have been resolved, stabilized (*i.e.*, no worsening of condition), or until an acceptable explanation has been found.

## 12 DATA MANAGEMENT

---

### 12.1 DATA COLLECTION PROCEDURES

The results from the clinical assessments will be recorded in the source data file by the Investigator or their authorized designee and then captured in the case report forms (CRFs), unless otherwise specified in the final protocol. Trained study personnel will be responsible for capturing the data from the observations, tests, and assessments specified in the protocol and in the source documents. Study personnel will transfer the data to the CRFs.

The Investigator has ultimate responsibility for the collection and reporting of all data related to the clinical study and ensuring that the data are accurate, authentic/original, legible, timely (contemporaneous), enduring, and available when required. Any corrections made to source documents must be clearly recorded, without obscuring the original values and be accompanied by the date of change, reason for change, and identification of the person making the change. CRF data will be verified against the source documents at the study site by appropriate staff. Instances of missing or unclear data will be discussed with the Investigator for resolution.

## 12.2 PROTOCOL DEVIATIONS / NONCOMPLIANCE

Protocol deviations are defined as deviations from the study procedures as defined in this document, whether intentional or unintentional that may affect the participant's rights, safety, or well-being and/or the completeness, accuracy and reliability of the data.

Noncompliance that meets the above definition must be reported to the IRB within 10 days of becoming aware of the noncompliance.

## 12.3 DATA CAPTURE

All data are collected from participants using paper documents or an electronic data capture system. All applicable data, as specified in the protocol, will be transferred to the database or applicable Case Report Forms.

### 12.3.1 Salesforce.com

Data will be collected for recruitment and screening purposes as stated within an Advarra IRB generic recruitment protocol. Unrelated to that protocol, pre-screening questionnaires will be attached to potential participant's records on whether they qualify or are disqualified for this study. Questionnaires utilized for this study will be permanently attached to that potential volunteer's record unless that information is requested to be removed by the participant.

### 12.3.2 Survey Monkey

Survey Monkey uses some of the most advanced technology for Internet security that is commercially available today. This Security Statement is aimed at being transparent about our security infrastructure and practices, to help reassure that data is appropriately protected. Visit Survey Monkey privacy policy for more information on data handling.

All Survey Monkey information systems and infrastructure are hosted in world-class data centers. These data centers include all the necessary physical security controls you would expect in a data center these days (e.g., 24x7 monitoring, cameras, visitor logs, entry requirements). SurveyMonkey has dedicated cages to separate our equipment from other tenants. In addition, these data centers are SOC 2 accredited.

### 12.3.3 Short Message Service (SMS) Messaging

SMS Messaging will be utilized for the delivery of a hyperlink to a mobile device to collect study data. This data will be collected utilizing an electronic survey. The service utilized for these messages is textit.in.

### 12.3.4 Medrio

All smoking behavioral and self-report measures will be captured initially using Medrio. Medrio is an electronic data collection system that records and performs analysis and reporting of data. Participant data will be kept within Medrio's secure servers and may only be transmitted through a secure (SSL) download to our local server. Medrio's servers are protected by high-end firewall systems, with vulnerability scans performed regularly. All services have quick failover points with redundant hardware, and complete encrypted backups are performed regularly. Medrio uses Transport Layer Security (TLS) encryption (SSL or HTTPS) for all transmitted internet data. All information collected within Medrio is compliant with 21 CFR 11 requirements.

## 12.4 DATA HANDLING

Data of all participants enrolled including screening failures and AE/SAEs during the study (from the time of informed consent to the end of the study of the participant) will be captured in the source documents.

# 13 PLANNED STATISTICAL METHODS

---

All data measures (e.g., withdrawal symptoms questionnaires, smoking history, smoking diaries, etc.) are captured initially using paper or an electronic data capture system. Verified data files will be analyzed using Statview or SAS (Statview, SAS Institute, Cary NC). Data will be inspected for outliers and if sufficiently extreme (Chauvenet's criterion, after verifying normality of distributions) will be censored from the data analysis.

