### 2.3 CHANGE IN REWARDING EFFECTS OF SMOKING CIGARETTES

Secondary analyses will evaluate the hypothesis that enjoyment of smoking after meals is attenuated by zonisamide/bupropion treatment. The smoking satisfaction scale of the mCEQ-E will be compared between cigarettes smoked after meals versus all others smoked during the day, examining how this difference changes after zonisamide/bupropion usage. Additionally, the proportion of participants who report smoking after meals, while reporting not smoking at other times, will be compared between the first week and the weeks after zonisamide/bupropion usage.

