#### 8.2.14.2 ***Modified Cigarette Evaluation Questionnaire-Extended (mCEQ-E) and Modified Electronic Cigarette Evaluation Questionnaire-Extended (mECEQ-E)***

The Cigarette Evaluation Questionnaire was initially developed in the PI's laboratory and used in numerous studies to assess the effects of pharmacological treatments on the rewarding effects of cigarette smoking. The mCEQ-E will be utilized to assess the degree to which participants experience the reinforcing of smoking, providing five subscale scores: smoking satisfaction (satisfying, tastes good, enjoy smoking), psychological rewards (calms down, more awake, less irritable, helps concentrate, reduces hunger), aversion (dizziness, nauseated), enjoyment of respiratory tract sensations (single-item assessment), craving reduction (single-item assessment). Participants will be asked to assess the 12 items of the questionnaire on a 7-point scale, ranging from "not at all" to "extremely". These 12 items will be asked for the "first cigarette smoked", "cigarette immediately after a meal", and "all other cigarettes." The e-cigarette version of this questionnaire (mECEQ-E) will also be used.

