## 8.6 SMS MESSAGING

8.6.1 Daily SMS Message (after screening, prior to V2) – Participants will receive a text with a link to a survey to access the following:

- Have you smoked any combustible cigarettes today?
  - If yes, how many cigarettes did you smoke?
  - What was your favorite cigarette of the day?  
1-First one, 2-One immediately after a meal, 3-Any other cigarette

8.6.2 Daily SMS Message (From Visit 2) -- Participants will receive a text with a link to a survey to assess the following:

- Have you smoked any combustible cigarettes today?
  - If yes, how many cigarettes did you smoke?
  - Which cigarette did you smoke today? (If only 1 cigarette is reported)  
1-First one of the day, 2-One immediately after a meal, 3-Any other cigarette
  - What was your favorite cigarette of the day? (Of more than 1 cigarette is reported)  
1-First one, 2-One immediately after a meal, 3-Any other cigarette
- Have you used your e-cigarette today?
  - If yes, how many times did you use your e-cigarette today?
- Did you take your study drugs this morning? (After Visit 3)

8.6.3 6-Month follow up SMS Message -- Participants will receive a text with a link to a survey to assess the following:

- Have you smoked a combustible cigarette since your last visit?
  - If yes, are you still smoking combustible cigarettes right now?
  - How many combustible cigarettes do you smoke per day on average?
- Have you used an e-cigarette since your last visit?
  - If yes, are you still using an e-cigarette?
  - How often do you use an e-cigarette?
- Have you used any other nicotine containing products (other than e-cigarettes) since you last visit?

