### 13.1.2 Change in Rewarding Effects

Change in reported rewarding effects of smoking for cigarettes smoked in the morning, after meals and at other times during the day will be compared.

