Appendix 9 – modified Cigarette Evaluation Questionnaire - Ext (mCEQ-E)

### CIGARETTE EVALUATION QUESTIONNAIRE- Ext modified

Have you smoked any cigarettes since your last visit?

- No: Skip questionnaire
- Yes: Please answer the following questions based on the **FIRST** cigarette you smoked on the last day you smoked.

	Not at all	Very little	A little	Moderately	A lot	Quite a lot	Extremely
1. Was it satisfying?							
2. Did it taste good?							
3. Did it make you dizzy?							
4. Did it calm you down?							
5. Did it help you concentrate?							
6. Did it make you feel more awake?							
7. Did it reduce your hunger for food?							
8. Did it make you nauseated?							
9. Did it make you feel less irritable?							
10. Did you enjoy the sensations of the smoke in your throat and chest?							
11. Did it immediately reduce your craving for cigarettes?							

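### Section 13's outlier rule deletes verified values with no evidence of error; an assumed 5% t-test on screened change scores runs at about 7% (n=25) or 6% (n=50)

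*Combined protocol and SAP*

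**What the plan says.** The opening paragraph of Section 13 has verified files analysed and the data inspected for outliers. For values extreme by Chauvenet's criterion, it reads: "after verifying normality of distributions) will be censored from the data analysis". Censoring here can only mean leaving the value out. The paragraph speaks of all measures, gives questionnaires, smoking history and diaries as examples, and exempts none.

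The data have by then been checked. Section 12.1 states: "CRF data will be verified against the source documents at the study site by appropriate staff".

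The continuous analyses that the rule reaches are mainly those of rewarding effects:
- Section 2.3 compares mCEQ-E satisfaction for after-meal cigarettes with that for all others, "examining how this difference changes after zonisamide/bupropion usage".
- Section 13.1.2 states: "Change in reported rewarding effects of smoking for cigarettes smoked in the morning, after meals and at other times during the day will be compared".
- The satisfaction score comes from three 7-point items: "smoking satisfaction (satisfying, tastes good, enjoy smoking" (Section 8.2.14.2).
- Appendix 9 opens with "Have you smoked any cigarettes since your last visit", and a participant who answers no skips the form.

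The plan does not name the normality test or say what happens if it fails. It does not say whether the rule acts on recorded scores or on derived changes, or whether it is applied once or repeatedly. No analysis with all values kept is planned.

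**The concern.** Chauvenet's criterion is set so that a clean normal sample is expected to hold half a value beyond the cut-off. It therefore discards good data routinely. Checking normality first does not help: it points the rule at the variables whose extreme values are most likely to be real.

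Trimming both tails and then analysing the remainder as a complete sample understates the standard deviation. Intervals are too narrow, and a test can exceed its nominal level. How far it does so depends on choices the plan leaves open, and in an open-label, single-group study these could be made after the data are seen. At stake are the tests of the study's mechanism, namely change in the reward of after-meal smoking, and the withdrawal and dependence scales.

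**Working it through.** **Inputs.** The sample size is 25 or 50 (Section 3.1). The rule and the normality check come from Section 13, and the main contrast from Section 2.3. The documents give no error rate for these analyses, so there is no figure of the plan's own to reproduce.

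**Assumptions.** Two-sided 5% t-test; Shapiro-Wilk p>0.05 counts as passing the check; a single pass using the sample mean and the n-1 SD; all values kept if the check fails.

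**Step 1: cut-off.** A value is dropped when n × P(|Z|>d) < 0.5, so d = Φ⁻¹(1 − 1/(4n)).
- n=25: Φ⁻¹(0.99) = 2.326 SD
- n=50: Φ⁻¹(0.995) = 2.576 SD

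**Step 2: how often clean data lose a value.** Each normal value lies beyond the cut-off with probability 1/(2n). With known mean and SD, the chance of at least one such value is 1 − 0.98²⁵ = 39.7% (n=25) or 1 − 0.99⁵⁰ = 39.5% (n=50). With sample mean and SD, simulation gives 33.6% and 35.8%. About 95% of normal samples pass the check, so it restrains little: 30.2% and 32.6% pass and lose at least one value.

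**Step 3: change scores screened.** Normal data, no true effect, 60,000 samples per n (Monte Carlo SE 0.1 point):

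| Handling | n=25 | n=50 |
|---|---|---|
| All values kept | 5.0% | 5.0% |
| Single pass, after the check | 7.2% | 6.3% |
| Single pass, no check | 7.7% | 6.5% |
| Repeated passes, after the check | 7.9% | 6.7% |

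A separate run of 40,000 samples gave 7.1% and 6.1% for the single pass after the check. Among samples that pass the check, the interval is 0.961 (n=25) or 0.974 (n=50) of its full-data width.

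**Step 4: each visit's score screened, then a paired t-test.** 20,000 samples per setting (Monte Carlo SE 0.16 point; all values kept 4.7-5.3%):

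| Within-person correlation | n=25 | n=50 |
|---|---|---|
| 0.3 | 6.6% | 5.7% |
| 0.5 | 6.1% | 5.9% |
| 0.7 | 5.5% | 5.5% |
| 0.9 | 5.0% | 4.8% |

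**Step 5: bounded satisfaction scores.** These are simulated as means of three rounded ratings from 1 to 7. For a single visit, with assumed mean 4-6 and SD 1-2, 4-27% of variables pass the check and lose a value at n=25, and 0-27% at n=50.

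The Section 2.3 contrast is the change in (after-meal minus other) satisfaction, built from four such scores per person. With assumed SD 1.5, and six settings of 7,500 samples each:

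| What is screened | n=25 | n=50 |
|---|---|---|
| The contrast | 6.6-7.4% (average 7.0%) | 5.1-6.5% (average 6.0%) |
| Each of the four scores | 4.9-5.4% (average 5.2%) | 4.5-5.2% (average 4.9%) |
| Nothing, all kept | average 5.0% | average 4.8% |

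**Step 6: fewer respondents.** Participants who have not smoked skip the mCEQ-E, so its n can fall below 25. With normal change scores screened after the check, the error is 7.5% at n=20 and 7.9% at n=15. Purely as an illustration, since no V7-only test is planned, 25 − 16 = 9 remaining smokers would give 9.0%.

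**The case against.** The strongest reply is that the 7% belongs to one of two readings. Section 13 speaks of captured measures and verified files, so the natural object of screening is the recorded score. On that reading the Section 2.3 contrast stays at about 5%. This is correct, and it is why the error rate is given as a range. The plan does not settle the reading, though, and the recorded-score reading still deletes verified answers.

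Next, the test, alpha, sidedness, normality check and number of passes are all assumed. The Section 2.3 hypothesis is directional, and a one-sided 5% test on screened change scores gives 6.5% (n=25) and 6.1% (n=50). The excess is then about 1.5 and 1.1 points, smaller but still present. The rates are conditional; the absence of an all-values analysis is not.

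The effect is also small: on average 0.32 values per variable are removed at n=25 (0.32/25 = 1.3%) and 0.35 at n=50 (0.35/50 = 0.7%). The decision to advance or stop rests only on switching counts. Both points stand, and they limit how much weight this issue carries.

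Finally, the rule is named in advance and is objective, and source verification cannot catch a mistyped but plausible SMS count. That is true. However, a cut at 2.3 to 2.6 SD cannot tell such a typing error from a genuine heavy day. Reporting the results with and without extremes would answer much of the concern, provided the plan says which one governs.

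**Conclusion.** The concern holds. Section 13 removes verified values for extremeness alone, and nothing elsewhere in the document offsets this. For continuous secondary measures that pass the normality check, a 5% test of change runs between about nominal and about 2 points too high with a single pass. If change scores are screened it is 7.2% at n=25 and 6.3% at n=50; repeated passes raise these to 7.9% and 6.7%. Intervals on change scores are about 4% or 3% too narrow. The rates rest on the assumed t-test, level, normality check and score distributions. The binary switching outcome, the 64% and 56% thresholds and 6-month abstinence are untouched, so the point should be corrected but does not threaten the study's main decision.

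**What to change.** Replace the outlier sentence in Section 13 with:

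> All verified values are retained in the main analysis. A value is corrected or removed only if source verification shows a recording error or it lies outside a pre-specified possible range (for example, an impossible SMS count). Any analysis excluding extreme values is a labelled sensitivity analysis (one pass, on the analysed change score), and the analysis of all values governs.

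Add a short list of possible ranges for the counts that participants enter themselves, such as the Section 8.6 item "If yes, how many cigarettes did you smoke". Section 12.3.3 says of the SMS responses: "This data will be collected utilizing an electronic survey". Range limits are therefore the practical safeguard against typing errors there.

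The cost is one sentence and that list, with no extra participants or data. On change scores, intervals widen by about 4% at n=25 (1/0.961 = 1.04) and 3% at n=50 (1/0.974 = 1.03), and the assumed test returns to about 5%. Odd but possible values stay in the main analysis, and the sensitivity analysis shows their influence.

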## 13.1 OUTCOMES

### 13.1.1 Switching Outcome

Complete switching from combustible cigarette use at each time point will be defined by a self-report of no cigarette smoking (not even a puff) since the prior session, confirmed by an expired air CO reading of less than 5 ppm. The primary switching outcome will be smoking abstinence during weeks 8-11 post-switching date. An intent-to-treat approach will be taken in which any participants lost to follow-up after the point of randomization, or who have smoked during weeks 8-11 will be counted as having not completely switched to e-cigarette use. A secondary outcome will be 7-day point abstinence at 6 months post-switch. The main goal of the 6-month follow-up is to assess the persistence of switching to e-cigarettes. The main hypothesis to be evaluated in this pilot study is that the rate of complete switching to e-cigarette use will be greater than the historical benchmark of 45% smoking abstinence expected with varenicline when it is used in smoking cessation treatment.

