## 2 STUDY OBJECTIVES AND ENDPOINTS

### 2.1 COMPLETE SWITCHING FROM CC TO HALO G6

The primary switching outcome will be smoking abstinence during weeks 8-11 post-quit date. This will be defined as self-report of no cigarette smoking (not even a puff), confirmed by an expired air CO reading of less than 5 ppm.

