## 8.5 SCHEDULE OF EVENTS

Visit Assessments and Procedures		Screening Session	Baseline Cig Data Collection	Laboratory Sessions							Product Use Period
				V2	V3	V4	V5	V6	V7	13 Weeks	
		V1								PM SMS	
Informed Consent and Guidance		•									
Inclusion/Exclusion Criteria		•									
Enrollment/Randomization				•							
Prior and Concomitant Medication		•		•	•	•	•	•	•		
Questionnaires	Smoking History Questionnaire	•									
	Registration Form	•									
	Employment History			•							
	Medical History/Review of Systems	•									
	Payment Verification Form	•		•	•	•	•	•	•		
	Reasons to Smoke			•					•*		
	Modified Cigarette Evaluation Questionnaire Extended (mCEQE)			•	•	•	•	•	•		
	Modified e-Cigarette Evaluation Questionnaire Extended (meCEQE)				•	•	•	•	•		
	The Fagerström Test for Nicotine Dependence (FTND)			•	•				•		
	Shiffman-Jarvik Withdrawal Scale			•	•	•	•	•	•		
	Assessment of Behavioral OUTcomes (ABOUT)			•	•				•		
	Patient Health Questionnaire (PHQ-9)	•		•	•	•	•	•	•		
	e-Cigarette Usage and Smoking Status (via daily SMS text)			•						•	
	Medication Adherence (via daily SMS text)									•	
	Safety Laboratories		•								
Serum Pregnancy Test (Females)		•									
Urine Pregnancy Test (Females)				•	•	•	•	•	•		
Urine Drug Screen		•									
CO Breath Test		•		•	•	•	•	•	•		
ECG		•									
Vitals	Blood Pressure	•		•	•	•	•	•	•		
	Heart rate	•		•	•	•	•	•	•		
	Temperature	•									
	Respiratory rate	•		•	•	•	•	•	•		
	Weight	•		•	•	•	•	•	•		
	Height	•									
Physical Examination		•		•#	•#	•#	•#	•#	•#		
Halo Assessment and Questionnaire				•							
Collect Used/Unused Halo products					•	•	•	•	•		
Dispense Halo products				•	•	•	•	•			
Collect Used/Unused Blister Packs					•	•	•	•			
Dispense Study Drugs in Blister Packs					•	•	•	•			

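### The primary outcome requires no smoking, not even a puff, but no smoking-status item shown asks about puffs, and the plan does not say which item scores the outcome

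*Combined protocol and SAP*

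**What the plan says.** Section 2.1 defines the primary outcome, abstinence during weeks 8 to 11, as "self-report of no cigarette smoking (not even a puff), confirmed by an expired air CO reading of less than 5 ppm". Section 13.1.1 repeats the standard and adds the recall interval: switching is "defined by a self-report of no cigarette smoking (not even a puff) since the prior session". The puff standard appears in these two places only.

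Three items shown in the document could supply the self-report:

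- **Daily text (Section 8.6.2):** "Have you smoked any combustible cigarettes today". A Yes leads to a count of cigarettes and one short follow-up.
- **mCEQ-E opening line (Appendix 9, scheduled V2 to V7):** "Have you smoked any cigarettes since your last visit". The negative option reads "No: Skip questionnaire".
- **Reasons to Smoke opening line (Appendix 16, scheduled at V2 and V7):** asks about any cigarettes since the switch day. A No skips the form. A footnote to Section 8.5 ties the V7 administration to current product use, so it may be conditional.

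The Section 8.5 schedule carries smoking status on one line, "e-Cigarette Usage and Smoking Status (via daily SMS text"), and lists no separate abstinence question at visits. CO is measured at each session (Sections 8.2.8 and 8.5).

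**The concern.** The definition and the instruments set different thresholds. The definition fails a participant for one puff. The items ask about cigarettes, and the text follow-up counts them. Someone who took a few puffs of another person's cigarette may not regard that as having smoked a cigarette. That person could answer No each time in good faith and still not meet the definition.

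CO does not close the gap, because a reading on the visit day says little about puffs on earlier days of the interval. The strict part of the definition therefore rests on self-report.

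The misclassification runs one way, since a missed puff turns a non-switcher into a switcher. The decision rule is also sensitive to single participants. Under Sections 3.1.1 and 3.1.2, 16/25 advances the treatment to larger randomized trials at once, while 15/25 enrols 25 more. One participant is 1/25 = 4 percentage points.

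A secondary point is that on both visit forms a No is the shorter path. If either opening line were the only evidence of abstinence, the form's layout would favour the answer that scores as success.

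**Working it through.** **Definition against items.**

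| Source | Interval covered | Asks about puffs? | Effect of No |
|---|---|---|---|
| Definition, Section 13.1.1 | Since prior session | Yes | n/a |
| Daily text, 8.6.2 | Today | No | Cigarette follow-ups not asked |
| mCEQ-E opening line, Appendix 9 | Since last visit | No | Whole form skipped |
| Reasons to Smoke opening line, Appendix 16 | Since switch day | No | 13 items skipped |

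The intervals are adequate. Consecutive daily texts cover the window, the mCEQ-E covers each inter-visit interval, and at V7 the Reasons to Smoke question includes the whole time since V6. The gap is in what is asked. No row after the first carries the puff standard, and no section says which row scores the primary outcome.

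**Length of the skipped forms.** Section 8.2.14.2 says "Participants will be asked to assess the 12 items of the questionnaire on a 7-point scale", for three occasions: 12 × 3 = 36 items. The after-meal block has its own skip, so a Yes leads to between 24 (36 − 12) and 36 items. A No leads to none.

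**The decision rule as planned.** Inputs are the thresholds of 16/25, 13 to 15 of 25 to continue, and 28/50 (Sections 3.1.1 and 3.1.2), and the 45% benchmark (Section 13.1.1). With X1 and X2 independent Binomial(25, p):

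P(advance) = P(X1 ≥ 16) + Σ over k = 13 to 15 of P(X1 = k) × P(X2 ≥ 28 − k)

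At p = 0.45 this is 0.0440 + 0.0436 = 0.0876. That is broadly in line with the overall Type I error of about 10% in Section 3.1.3.

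**Illustration of missed puffs.** Let m be the share of true non-switchers counted as switched. The documents give no value for m, so the values below are assumptions. With a true strict rate of 45%, the counted rate is 0.45 + 0.55m. Among 25 participants, the expected number misclassified is 25 × 0.55 × m = 13.75m.

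| m (assumed) | Counted rate | Expected misclassified in 25 | P(advance) |
|---|---|---|---|
| 0 | 0.450 | 0 | 8.8% |
| 2% | 0.461 | 0.28 | 11.3% |
| 5% | 0.4775 | 0.69 | 16.0% |
| 10% | 0.505 | 1.38 | 26.3% |

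Fewer than one misclassified participant in 25, on average, is enough to take the chance of advancing above the stated error rate.

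**The case against.** The best defence is the daily text. It is the source labelled as smoking status, its one-day recall covers weeks 8 to 11, a Yes costs only two short follow-ups, and the $5 payment does not depend on the answer given. Many people who had taken a puff might still answer Yes. To be misclassified, a participant must have had puffs only, reported no cigarette throughout the window, and shown CO below 5 ppm, which may be uncommon. All of this stands and limits the likely size of the problem. It does not supply the puff standard, which the text omits like the other items.

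A reader might infer more than the documents support:

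- **That the mCEQ-E opening line is the only visit item covering the interval, or the item that scores the outcome.** Reasons to Smoke also covers the interval at V7, and the plan names no scoring item. No evidence shows that skipping drives answers. The burden argument is therefore only a reason not to rely on either opening line alone.
- **That nothing in the trial asks about puffs.** Section 13 mentions smoking diaries and Section 12 mentions case report forms, neither of which is reproduced. The claim extends only to the items shown.
- **That a single CO reading covers the window.** CO is taken at every session, and the text shown does not give the timing of V4 to V6, so the number of readings in weeks 8 to 11 cannot be established.
- **That the false-positive rate is in fact above 10%.** The values of m are assumed. Any bias relative to the 45% benchmark also depends on how abstinence was measured there, which the plan does not say. Similar questions would make the relative bias small or nil.

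**Conclusion.** The point holds as a mismatch between the printed primary definition and the printed items, together with an unnamed scoring source. The trial as written could not show that its strict criterion was met. Any error from this source raises the measured switching rate.

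The size is unknown. The rise from 8.8% to between 11.3% and 26.3% shows how sensitive the rule is, and is not an estimate of bias. It rests on a true strict rate of 45%, independent participants, the thresholds applied exactly as stated, and assumed misclassification of 2% to 10% of non-switchers. The finding should be corrected because the remedy is cheap and the decision can turn on one participant. It does not invalidate the design.

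**What to change.** 1. In Section 8.6.2, add the words *even a puff* to the daily smoking question.
2. At V4 to V7, add one standalone item asked before the mCEQ-E: *Since your last visit have you smoked any cigarette, even one puff? If yes, on which dates?*
3. In Section 13.1.1, state that the primary outcome is scored from that item together with the daily texts and CO.
4. In the same place, state that a Yes from any source, including the opening lines of the mCEQ-E and Reasons to Smoke, counts as smoking when it falls in the window. A No on either opening line is not sufficient evidence of abstinence. Ignoring those lines altogether would be wrong, because a Yes there is direct evidence of smoking. The dates from item 2 place such a Yes inside or outside weeks 8 to 11.

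The cost is one wording edit, one added line on the case report form and a short scoring statement, with IRB review and approval before implementation (Section 14.1). No treatment or decision threshold changes. The measured switching rate may be slightly lower.
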